#### 4.4.1. Soft commitment device

Patients randomized to the commitment device arm will be asked to visit the Way to Health platform. There, they will identify a support person, a family or friend who they speak to frequently and who is invested in their health. They will then complete a series of questions intended to create implementation intentions. Specifically, they will pick a time for their fast to begin each 24-hour period and a time for their fast to end. They will also develop strategies to deal with hunger arising during a fast period. After this process, they will sign a contract pledging to adhere to the 16:8 time-restricted feeding dietary pattern, and acknowledging that their support person will receive a copy of the contract and weekly updates about their adherence to the regimen.

For the next 12 weeks, participants in this arm will receive reminder text messages two times daily via Way to Health: Once at the start of their fast period and once during the meal that they skip during the fast period. Each week, participants and their support partner will also receive a text message noting how many days in the previous week they successfully fasted for at least 16 hours. After the 12 week intervention, these text messages will stop, but for the entire 18-week period, participants in this arm will receive the same text messages as the attention control arm: A daily text message asking if they fasted for at least 16 hours over the previous 24 hours, and a weekly text message asking for weight and blood pressure results.

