# 3. Study Design

#### 3.1. General Overview

The IFAST study is a two-arm randomized controlled trial aimed at evaluating whether a soft commitment device increases uptake and adherence to an intermittent fasting dietary pattern compared with control in patients with hypertension and obesity. The study will randomize 34 patients with hypertension and obesity to a 12-week intervention employing a commitment pledge, involvement of a supportive partner, setting of implementation intentions, and multiple daily reminder text messages or to an attention control involving daily text messages alone.

Following the intervention, there will be a 6-week follow-up period (see study protocol figure below).

The study will be conducted using Way to Health, a research information technology platform at the University of Pennsylvania used previously for behavioral interventions.

After institutional review board (IRB) approval of the study, patients who meet the eligibility criteria will be approached in select cardiology clinics and invited to participate. Those who qualify and express interest will provide informed consent to the study procedures via the Way to Health platform. All patients will receive a blood pressure cuff and scale, which will be used to measure blood pressure and weight weekly. Within the Way to Health platform, patients will be randomized to the intervention or control arms. All other management decisions are completely at the discretion of the care providers. Data capture will include:

- **Baseline case report form** (for each patient) collecting clinical information abstracted from the medical record
- **Baseline survey** collected via the Way to Health platform including psychometric questions, dietary patterns, and experiences with weight loss and dieting
- Daily adherence to an intermittent fasting dietary pattern collected via self-report from text messages
- Weekly weight and blood pressure measurement collected via self-report from text messages

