#### 4.4. Study Arms

#### 4.4.1 Attention control

These patients will be instructed via text message and email to fast at least 16 hours per day every day. For the next 16 weeks, they will receive a daily text message via the Way to Health

platform asking if they fasted for at least 16 hours over the past 24 hours. If they fail to respond, reminder text messages will be sent. Once per week, they will receive a text message asking them to weigh themselves and check their blood pressure, and reply with the results via text message

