#### 5. Statistical Methods

# 5.1 Primary and secondary outcome measures

The study's primary outcome measure is adherence to the IF regimen, captured via daily text message, over 18 weeks, expressed in days per week.

Secondary outcome measures will include:

- 1) Adherence to the IF regimen over 12 weeks
- 2) Change in systolic blood pressure from baseline to 12 weeks and 18 weeks
- 3) Change in weight from baseline to 12 weeks and 18 weeks

Exploratory analyses will compare change in blood pressure and weight in patients that were adherent to IF  $\geq$  4 days per week vs.  $\leq$  4 days per week

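### Self-reported adherence is shared with a partner in one arm only, and no outcome isolates weeks 13-18, when that sharing has stopped

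*Combined protocol and SAP*

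**What the plan says.** Section 5.1 defines the primary outcome as "adherence to the IF regimen, captured via daily text message, over 18 weeks, expressed in days per week". The first secondary outcome is "Adherence to the IF regimen over 12 weeks". No adherence outcome covers the weeks after the intervention on their own.

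Section 3.1 gives the data source: "Daily adherence to an intermittent fasting dietary pattern collected via self-report from text messages". Blood pressure and weight come the same way: "Weekly weight and blood pressure measurement collected via self-report from text messages".

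Section 4.4.1 (Soft commitment device) has participants name a support person and sign a pledge, "acknowledging that their support person will receive a copy of the contract and weekly updates about their adherence to the regimen". During the 12-week intervention, "Each week, participants and their support partner will also receive a text message noting how many days in the previous week they successfully fasted" for the required time. Then: "After the 12 week intervention, these text messages will stop". The daily question continues in this arm to week 18. Controls have no partner and no pledge. Their section says "For the next 16 weeks, they will receive a daily text message via the Way to Health" platform, and Section 4.5 also places the end of the study at 16 weeks.

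Section 5.3 scores a day without a report as non-adherent and compares the arms by t test.

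**The concern.** In the commitment arm, the reply that forms the outcome is also the information sent to the partner. Section 1.3 explains that an interpersonal commitment works through the prospect of disappointing that partner. A participant can avoid this by fasting or by answering yes. Because a missing reply counts as a day not fasted, greater willingness to reply also raises the score, and this arm gets extra reminders and weekly feedback as well as the daily question.

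So a higher mean in the commitment arm has two possible sources: behaviour and reporting. Objective 1 (Section 2) is about uptake of and adherence to fasting, so the distinction matters for the main conclusion. The design offers a partial check, because partner updates and reminders stop after week 12 while the daily question is meant to go on. Section 5.1 does not use it. Its two windows overlap, and both include the whole period of partner updates.

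**Working it through.** **Inputs.** 17 per arm, target difference 1 day/week, stated power 90% (Section 5.2). The SD is printed as below 1.24; this may be 1 followed by citation 24, so both 1 and 1.24 are used. The test is a t test (Section 5.3); level and sidedness are not stated, so two-sided 5% is assumed. Partner updates cover weeks 1-12 (Section 4.4.1) and follow-up is 6 weeks (Section 3.1). The amount of over-reporting, *b* days/week, is an assumption; the documents give no figure.

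**1. The plan's own figure.** The noncentrality is difference / (SD × √(2/17)), with √(2/17) = 0.343 and 32 degrees of freedom. For 1 day/week:
- SD 1: 1/0.343 = 2.92, power 80.7%.
- SD 1.24: 1/(1.24 × 0.343) = 2.35, power 62.6%.

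Two-sided power of 90% needs an SD of about 0.87. At SD 1 a one-sided 5% test gives 88.7%. The stated 90% is thus not reproduced at 1.24. That is a separate matter; here it only means the illustration is shown for SD 0.87, 1 and 1.24.

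**2. Effect of over-reporting confined to weeks 1-12, with no true effect.** The 12-week difference is *b*. The 18-week difference is *b* × 12/18:
- *b* = 0.5: 0.5 × 12/18 = 0.33
- *b* = 1.0: 1.0 × 12/18 = 0.67

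**3. Chance of a significant t test**, assuming the SD is the same for both windows and is not changed by the over-reporting:

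| *b* | Outcome | Shift | SD 0.87 | SD 1 | SD 1.24 |
|---|---|---|---|---|---|
| 0.5 | 18-week (primary) | 0.33 | 19% | 16% | 12% |
| 1.0 | 18-week (primary) | 0.67 | 58% | 47% | 33% |
| 0.5 | 12-week (secondary) | 0.5 | 37% | 29% | 21% |
| 1.0 | 12-week (secondary) | 1.0 | 90% | 81% | 63% |

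**4. What weeks 13-18 would show.** With A12 and A18 the between-arm differences over 12 and 18 weeks, the difference over weeks 13-18 is (18 × A18 − 12 × A12)/6 = 3 × A18 − 2 × A12.
- Over-reporting of 1 day in weeks 1-12 only: 3 × 2/3 − 2 × 1 = 0.
- True effect of 1 day that persists to week 18: 3 × 1 − 2 × 1 = 1.
- True effect of 1 day that ends at week 12: 3 × 2/3 − 2 × 1 = 0, the same as the first case.

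A difference that persists therefore cannot be put down to the partner updates while they were running. A null result is ambiguous.

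**5. The 16/18-week conflict.** Suppose both arms fast 4 days/week (assumed), but controls are asked for only 16 weeks. Weeks 17-18 then score zero in that arm.
- Weeks 13-18: control mean 4 × 4/6 = 2.67, spurious difference 4 − 2.67 = 1.33.
- Weeks 1-18: control mean 4 × 16/18 = 3.56, spurious difference 4 − 3.56 = 0.44.

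**The case against.** Several objections have force.

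- **Direction.** Someone who speaks often with the participant may deter false replies. This stands: the documents do not establish which way any bias runs.
- **Derivability.** The 12-week outcome isolates the period with updates, and the weeks 13-18 mean follows by arithmetic from the two named windows. True, but no contrast, test or interpretation of it is planned.
- **Diagnostic value.** A real effect may fade when reminders stop, and the pledge or a reporting habit may outlast week 12. This also stands, and limits the contrast to a supporting role.
- **Other outcomes.** Weight and systolic pressure at 12 and 18 weeks are not part of the partner updates described, so they give some independent information. They are also texted in by the participant, so the corroboration is weak.

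A reader might go further and infer that over-reporting of one day in seven would reproduce the whole 1 day/week target, with 81% (SD 1) or 63% (SD 1.24) of trials significant on the primary outcome. That requires over-reporting in all 18 weeks. Partner updates stop after week 12, so over-reporting tied to them yields 0.67 on the primary outcome, not 1.0. If it did continue beyond week 12, the weeks 13-18 contrast would not detect it.

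**Conclusion.** The point holds as a gap in interpretation. Adherence is unverified self-report, it is shared with a partner in one arm only during weeks 1-12, and no planned outcome isolates the weeks that follow. A positive 12-week or 18-week result cannot alone distinguish more fasting from more favourable or more complete reporting. The primary-outcome rates of 16% and 47% at SD 1 (12% and 33% at SD 1.24) show what assumed over-reporting of 0.5 and 1.0 day/week would do; they do not estimate what will happen.

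A reader might infer that the device changes only reporting, or that a positive result could not reflect real fasting. The documents support neither: they contain no data on misreporting. Nor can weeks 13-18 be treated as a clean test, for the reasons in step 4. Until the 16-week and 18-week statements are reconciled, it is not even settled that both arms are queried alike in that period.

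**What to change.** 1. Reconcile the 16-week period in Section 4.4.1 (Attention control) and Section 4.5 with the 18-week period in Section 4.4.1 (Soft commitment device) and Section 5.1, so that both arms are queried for the same time. The next step depends on this.
2. In Section 5.1, add self-reported adherence over weeks 13-18 as a secondary outcome, with the scoring and t test of Section 5.3. Report weeks 1-12 and weeks 13-18 side by side.
3. Describe the outcome as self-reported adherence wherever conclusions are stated.

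Two additions that may suggest themselves are not worth making. One is a rule that real fasting may be claimed if either the weeks 13-18 difference or the weight difference favours the device. With no true effect on either, and if the two were independent, one or the other would do so in 1 − 0.5 × 0.5 = 75% of trials. The other is an end-of-study questionnaire item marked as not shared with the partner: updates have already stopped by then, and it is again self-report.

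The cost is some wording and one more secondary comparison on data already planned. The result must be presented as supportive, with the two explanations for a null (fading effect, or reporting that changed when the updates stopped) stated in advance.

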#### 4.5. End-of-Study Questionnaire Completion

At the end of the 16-week study period, patients will be alerted by the Way to Health platform to return to the website to complete an end-of-study questionnaire regarding their experience with IF.

#### 5. Statistical Methods

# 5.1 Primary and secondary outcome measures

The study's primary outcome measure is adherence to the IF regimen, captured via daily text message, over 18 weeks, expressed in days per week.

Secondary outcome measures will include:

- 1) Adherence to the IF regimen over 12 weeks
- 2) Change in systolic blood pressure from baseline to 12 weeks and 18 weeks
- 3) Change in weight from baseline to 12 weeks and 18 weeks

Exploratory analyses will compare change in blood pressure and weight in patients that were adherent to IF  $\geq$  4 days per week vs.  $\leq$  4 days per week

#### 5.2. Sample Size

With 34 patients (17 per arm), we will have 90% power to detect a 1 day per week difference in adherence to IF, assuming a standard deviation in days fasted per week < 1.24 The study will

have  $\sim 50\%$  power to detect a 10 mmHg change in systolic and diastolic blood pressure (assuming a standard deviation of 15 mmHg) and a 3 kg weight loss (assuming a standard deviation of 5 kg).

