# 1.2. Effect of Intermittent Fasting on Metabolic Parameters

In contrast to the DASH diet, intermittent fasting (IF) is a dietary pattern that emphasizes temporal restriction of caloric intake rather than restricting the number of calories and/or changing the types of foods eaten. The simplest and most popular variation of IF involves restricting caloric intake to an 8-hour period each day, and consuming no calories for the other 16 hours (so-called 16:8 time-restricted feeding). In animal studies, IF has been shown to activate cellular pathways with potential disease-modifying benefits in a number of conditions. In small human studies, IF is associated with a reduction in SBP by 5-10 mmHg, LDL cholesterol by ~8 mg/dl, and weight by ~ 3 kg, though none of the studies of a time-restricted feeding regimen included concurrent controls. Some patients report that IF is easier to initiate and maintain than other dietary patterns, though this has not been tested empirically.

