# 2. Study Objectives

The objectives of this study are the following:

[figure not shown]
- 1. To determine the effect of a robust soft commitment device, incorporating both intra- and interpersonal commitments, on uptake and adherence to an intermittent fasting dietary pattern, as compared with control, in patients with hypertension and obesity
- 2. To determine the effect of the intervention promoting intermittent fasting on blood pressure and weight in patients with hypertension and obesity

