#### 6.6 Risk/benefit

## 6.6.1 Potential study risks

Both arms will be instructed to pursue an IF dietary pattern, which has been shown to be generally safe across multiple studies. Potential adverse effects of IF include irritability, hunger, difficulty with concentration, development of an eating disorder, disrupted sleep, dehydration and dizziness, and feelings of guilt and increased stress. There is a theoretical risk of hypoglycemia and pancreatitis. At the start of the study, patients will be given information on risks of IF and guidance on when to seek medical attention. They will also be encouraged to consume plenty of fluids during their daily fasting period. Patients on insulin or insulin secretagogues will be excluded from participation, limiting the risk of iatrogenic hypoglycemia, but patients with diabetes mellitus will be asked about episodes of hypoglycemia via weekly text messages, and all patients will be asked about hospitalizations and emergency room visits via weekly text messages.

Another potential risk of this study is a breach of participant confidentiality. We will minimize this risk by using secure data methods as described previously. Names and addresses will be stored in encrypted databases. These data will be viewable only by the respective participants, the study coordinator(s) and the project manager(s). All other members of the research team will be able to view only participant ID numbers. Even the study arms will be identified by code letters until both the statistician and PI agree that analysis is complete.

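### The ~50% power in section 5.2 is too high for weight on its own inputs (about 40%), and for both blood pressure and weight it assumes a between-arm difference as large as the effect cited for fasting itself, although both arms fast

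*Combined protocol and SAP*

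**What the plan says.** Section 5.2 gives the primary calculation as "With 34 patients (17 per arm), we will have 90% power to detect a 1 day per week difference in adherence to IF". It then puts at about 50% its "power to detect a 10 mmHg change in systolic and diastolic blood pressure (assuming a standard deviation of 15 mmHg) and a 3 kg weight" (reduction, SD 5 kg). It gives no significance level, no source for the 10 mmHg or the 3 kg, and no expected between-arm difference in blood pressure or weight.

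The only figures of that size elsewhere are in section 1.2: in small studies, "IF is associated with a reduction in SBP by 5-10 mmHg, LDL cholesterol by ~8 mg/dl, and weight by ~ 3 kg". The same sentence concedes that the time-restricted feeding studies had no concurrent controls.

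On the contrast, section 6.6.1 says "Both arms will be instructed to pursue an IF dietary pattern". Section 4.4 agrees: control patients are told to fast 16 hours daily, and device patients pledge to the 16:8 pattern. Section 5.3 compares change from baseline in blood pressure and weight between arms with mixed effects models. These are secondary outcomes in section 5.1, and they serve objective 2: "To determine the effect of the intervention promoting intermittent fasting on blood pressure and weight in patients with hypertension and obesity".

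**The concern.** The arms share the fasting instruction and differ in the commitment device. A between-arm difference of 10 mmHg or 3 kg would mean that the device, added to that shared instruction, produces as much as section 1.2 attributes to fasting itself. The same paragraph sizes the primary comparison on a gap of 1 fasting day per week. The two parts of section 5.2 therefore sit badly together, and nothing in the plan supports so large a difference between two fasting arms.

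What is at stake is how a null result is read. Someone told that power was about 50% may take a null as modest evidence against fasting or against the device. If the realistic figure is close to the type I error rate, a null carries almost no information on either. Separately, the same figure of about 50% is attached to two different standardised effects, 10/15 = 0.67 and 3/5 = 0.60, so it needs checking for each.

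**Working it through.** **Inputs.** From section 5.2: n = 17 per arm; SD 15 mmHg and 5 kg; effects 10 mmHg and 3 kg; a 1 day per week adherence difference. From section 1.2: 5-10 mmHg systolic and about 3 kg. Assumed: two-sided 5%, no dropout, and one change score per patient.

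**Step 1: reproduce the stated power.** The standard error of a difference in means is SD × √(2/17) = SD × 0.343.

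- Blood pressure: 15 × 0.343 = 5.145; 10/5.145 = 1.944. Normal formula: Φ(1.944 − 1.960) = 49.3%. Noncentral t, 32 df: 47.0%.
- Weight: 5 × 0.343 = 1.715; 3/1.715 = 1.749. Normal formula: Φ(1.749 − 1.960) = 41.7%. Noncentral t: 39.6%.

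So about 50% is right for blood pressure and about 8 to 10 points too high for weight. Other readings do not bring both to 50%. A one-sided 5% test gives 60-62% for blood pressure and 53-54% for weight. A within-group test of change gives 73% and 64% with 17 patients, or 97% and 92% with 34. The blood pressure figure fits a two-sample, two-sided, between-arm calculation.

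**Step 2: what a smaller contrast implies.** Assumption, not in the plan: the effect is proportional to days fasted, and the section 1.2 effect corresponds to 7 versus 0 days per week. A gap of g days then gives 10 × g/7 mmHg (5 × g/7 at the low end) and 3 × g/7 kg. Power by noncentral t:

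| Gap (days/week) | SBP, from 10 mmHg | Power | SBP, from 5 mmHg | Power | Weight | Power |
|---|---|---|---|---|---|---|
| 1 | 1.43 | 5.8% | 0.71 | 5.2% | 0.43 kg | 5.7% |
| 2 | 2.86 | 8.4% | 1.43 | 5.8% | 0.86 kg | 7.7% |
| 3 | 4.29 | 12.8% | 2.14 | 6.9% | 1.29 kg | 11.2% |
| 4 | 5.71 | 19.0% | 2.86 | 8.4% | 1.71 kg | 16.3% |
| 7 | 10.0 | 47.0% | 5.0 | 15.6% | 3.0 kg | 39.6% |

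Under this scaling only the 7-day row returns the effects used in section 5.2.

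**Step 3: departures from the assumption.** If the device alone achieved half of 10 mmHg and 3 kg, whatever the days fasted, power would be 15.6% for 5 mmHg and 13.6% for 1.5 kg. If repeated weekly readings halved both SDs, power at a 1-day gap would be 8.4% for 1.43 mmHg and 7.7% for 0.43 kg.

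**Step 4: precision.** The 95% confidence interval half-width is 2.037 × SD × 0.343, which is 10.5 mmHg and 3.5 kg. Each slightly exceeds the largest effect in section 1.2.

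**The case against.** The strongest reply has four parts.

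- **The small effects are not the plan's.** The plan states no dose-response and does not equate the section 1.2 figures with 7 versus 0 days. One day per week is a detectable difference, not a forecast. The device could also alter fast length or intake in ways that a yes/no count of 16-hour fasts misses. All of this stands. A reader might infer that the plan's own figures imply about 1 mmHg and 0.4 kg, but those values need a scaling that the plan does not contain. They belong in a labelled range.
- **The origin of 10 mmHg and 3 kg is inferred.** This also stands. Section 5.2 cites no source for them and applies 10 mmHg to diastolic pressure too, while section 1.2 covers systolic only. What the documents support is that the figures are as large as those cited for fasting, not that they were taken from there.
- **Objective 2 can still be addressed.** A reader might infer that these endpoints cannot answer it. As worded, it concerns the intervention that promotes fasting, and the randomised difference between arms validly estimates that. The weakness is precision. For the effect of fasting itself there is no non-fasting arm, and only the non-randomised exploratory comparison by days fasted bears on it.
- **The plan already admits low power, for secondary outcomes.** True, and it limits the severity. But 50% and 5-20% call for different readings of a null, and the weight figure is wrong on its own inputs.

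The half-widths are for a simple change score. The planned mixed model may do better or worse, and the plan gives no within-patient correlation from which to derive its precision.

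**Conclusion.** The point holds in a limited form. The weight power should be about 40%, not about 50%; this rests only on the plan's inputs and a two-sided 5% test. The blood pressure figure is arithmetically sound. For both outcomes the assumed difference is implausibly large for two arms given the same fasting instruction. Under proportional scaling, power is about 5-6% at a 1 day per week gap and, taking the upper end of section 1.2, 11-13% at 3 days and 16-20% at 4 days (normal and t formulas together). No departure tried in the working comes near 50%, so the conclusion does not depend on exact linearity. This concerns the statement and interpretation of secondary outcomes. It leaves the primary analysis and the sample size untouched.

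**What to change.** In section 5.2:

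- State the significance level and sidedness, and correct the weight power to about 40%.
- Say that 10 mmHg and 3 kg are as large as the effect cited for fasting itself, while both arms fast.
- Add power over a range of between-arm differences (for example, those implied by gaps of 1 to 4 days per week), with the proportional scaling labelled as an assumption.

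In section 5.3, report between-arm differences in blood pressure and weight as estimates with 95% confidence intervals, and state that a null result will not be read as no effect of fasting or of the device. The planned mixed model comparison can stay; making it purely descriptive is optional.

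The cost is wording and a less favourable stated power. No extra patients or data are needed.
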